6.6.2 Missing data

Adverse event data

Missing or partial date information for AEs will be replaced according to general Boehringer Ingelheim (BI) rules described in the BI guidance for handling of missing and incomplete AE dates ([2](#)).

Death date

For patients with a record of death captured on the electronic case report form (eCRF) with missing or only partial death date from all available sources, the death date will be derived. The latest date of any of the following dates will be used: event onset and end dates from either the AE page, or CEC adjudicated onset dates, by using also imputed AE dates, last day known to be alive + 1 day, range of possible days based on partial death date and date of trial completion.

Missing information on the date of first administration of trial drug

If the date of first drug administration is missing but the patient was randomised, the date of the first drug administration will be set to the date of randomisation. If the date of first administration is partially missing with the month and year present, the day will be set to the date of randomisation, if randomisation was in the same month. If randomisation was in the month prior to the first drug administration, the missing day will be imputed as the first day of the month.

Missing information on the date of trial medication stop

If the date is partially or completely missing, use the minimum of the following dates:

- end of treatment visit date, if available
- date of death
- trial completion (last contact date)
- longest extrapolated treatment duration (assuming 1 tablet/day)

In case of a partially missing date, if the imputed date is before the first day of the month/year given as the partial date, the first day of the month/year will be used.

All other cases need to be assessed by the trial team on an individual patient basis, using the points above as guidance.

Missing information on concomitant therapy or non-medication therapy dates

For incomplete date information, generally the midpoint of the possible interval will be used. If only the year is present, the day and month will be imputed as 01 July, if year and month is present the day will be imputed as 15. If the year is missing, the date will be considered missing.

If this leads to contradictions for the start or end date of a concomitant therapy (e.g. imputed end date before documented start date), a partial end date will be imputed as the end of the interval or a partial start date will be imputed as the start of the interval in the database to resolve this contradiction.

If it is unclear from the partial date, whether a therapy was before or after date of baseline, then it will be assumed, that the therapy started after baseline (similar to worst case rules applied for adverse events).

All other cases or conflicting cases resulting from these imputation rules need to be assessed by the trial team on an individual patient basis.

Missing measurement to confirm “sustained” decrease

An eGFR (Chronic Kidney Disease Epidemiology Collaboration (CKD-EPI)cr) reduction is

considered sustained, if it is determined by two or more consecutive post-baseline central laboratory measurements separated by at least 30 days (first to last of the consecutive eGFR values). If there is no additional measurement ≥ 30 days after the eGFR reduction is observed and the patient dies within 60 days of this measurement, then the eGFR reduction is also considered sustained.

Hospital discharge date

Missing hospital discharge dates will be replaced with the date of the last follow-up.

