Drug-induced liver injury (DILI)	No risk of DILI was identified for empagliflozin. However, DILI generally can be severe and lead to fatal outcome or need of liver transplant. Therefore, careful monitoring and assessment of patients for potential DILI is needed.	Parameters for potential liver injury are included in the safety laboratory. Cases of liver impairment are defined as an AESI. Severe cases of liver impairment are adjudicated. (see Sections 5.2.4 , 5.2.7 and 8.7; details are also described in the adjudication charter)
Renal safety	In clinical trials in patients with DM, the incidence of renal impairment was similar to placebo. An initial decrease of estimated glomerular filtration rate (eGFR) was seen in patients treated with empagliflozin, which improved during continuous treatment or discontinuation of empagliflozin.  Cases of renal impairment, including requiring dialysis, were reported in patients using SGLT2-inhibitors. Due to the renal mode of action and risk of volume depletion, the renal safety should be monitored.	Parameters for potential renal impairment are included in the safety laboratory. Cases of renal impairment are defined as an AESI (see Sections 5.2.4 and 5.2.7.1.4 ).
Women of childbearing potential (WOCBP)	The safety of empagliflozin in pregnant women was not established.	In accordance with international regulatory guidelines, WOCBP are excluded from trial participation unless they agree to use highly effective contraceptive method.  All WOCBP undergo pregnancy testing before being randomised.

Known and potential risks in healthy volunteers and patients with T2DM:

For the main risks, please refer to [Table 1.4.2: 1](#)

In clinical studies, empagliflozin was well tolerated in both healthy volunteers and patients with T2DM including patients with high CV risk. The frequency of overall adverse events (AEs), AEs leading to discontinuation and serious adverse events (SAEs) were comparable to placebo [[c01678844](#)].

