**6.2.2 Treatment period(s)**

After a final check of all in- and exclusion criteria, patients eligible will be randomised at Visit 2a using IRT. Randomisation can occur at the same day as the screening visit. All Visit 2a assessments must be performed before the first dose is taken in hospital. Assessments from Visit 2a will be used as baseline values.

Patients will undergo visit assessments as indicated in the [Flow Chart](#).

Patients will have further visits with a reduced number of assessments two and four days thereafter if they are still hospitalised (Visits 2b and 2c at Day 3 and 5).

The patients will return to the clinic for regularly scheduled Visits 3, 4 and 5 (EoT) on days 15, 30 and 90 respectively after randomisation as specified in the Flow Chart. These on-site visits will assess the occurrence of safety and efficacy endpoints, trial medication compliance (Visit 3, 4 and 5), concomitant therapy or intervention. The assessments at these visits can be performed post-dose. Patients should be instructed to take their medication on the morning of their visits at home like all days. Visits should be routinely scheduled at approximately the same time of day for each visit.

All other medications the patient is receiving should be taken as instructed by the physician. At any time during the treatment period, the HF background therapy is allowed to be adjusted and optimised according to local and international guidelines.

If any additional therapy is considered necessary for the patient's welfare during the treatment period it may be given at the discretion of the Investigator (see also restrictions in [Section 4.2.2](#)).

Patient reported outcome measures (first KCCQ, then PGI – Severity – Heart Failure Symptoms questionnaire) should be done first and laboratory samples should be taken at the end of each visit. All other measures should be performed after PGI-S and before laboratory sampling.

Proprietary confidential information © 2020 Boehringer Ingelheim International GmbH or one or more of its affiliated companies

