5.2.2 Secondary endpoints

[figure not shown]
Secondary endpoints are specified in the CTP Section 2.1.3. Regarding the CV death endpoint, adverse events on the eCRF death event form where the primary cause of death is CV death or unknown cause of death, will be classed as CV death.

Regarding the secondary endpoint “occurrence of HHF until 30 days after initial hospital discharge”, HHFs are defined as the subset of HFEs where the investigator has checked the hospitalisation tick box.

Regarding the secondary endpoint “occurrence of chronic dialysis or renal transplant or sustained reduction of $\geq 40\%$ eGFR Chronic Kidney Disease Epidemiology Collaboration Equation ((CKD-EPI)cr), or

- sustained eGFR (CKD-EPI)cr < 15 mL/min/1.73 m² for patients with baseline eGFR ≥ 30 mL/min/1.73 m²
- sustained eGFR (CKD-EPI)cr < 10 mL/min/1.73 m² for patients with baseline eGFR < 30 mL/min/1.73 m²,

the following applies: an eGFR (CKD-EPI)cr reduction is considered sustained, if it is determined by two or more consecutive post-baseline central laboratory measurements separated by at least 30 days (first to last of the consecutive eGFR values). Chronic dialysis is regarded as chronic if the frequency of dialysis is twice or more per week for at least 90 days. Chronic dialysis and renal transplant will be confirmed by medical review of data from the concomitant non-drug therapy eCRF page.

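### The death rule in SAP 6.6.2 can count an eGFR fall as sustained although central samples taken less than 30 days later show that it recovered

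*SAP*

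**What the plan says.** The renal secondary endpoint (Protocol 2.1.3) includes a sustained eGFR reduction of at least 40%, or a sustained eGFR below 15 or 10 depending on baseline. The SAP gives two routes to sustained.

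- **Standard route (SAP 5.2.2, repeated in 6.6.2).** The reduction must be "determined by two or more consecutive post-baseline central laboratory measurements separated by at least 30 days". On the natural reading, a recovered value in between breaks the run.
- **Death route (SAP 6.6.2, under the subheading on a missing confirmatory measurement).** A fall qualifies here given "no additional measurement ≥ 30 days after the eGFR reduction is observed and the patient dies within 60 days of this measurement". The SAP words this as an addition to the standard route, not as a limit on it.

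The death route has two conditions only. It does not ask that the reduced value be the last one, or that later values stay reduced. SAP 5.2.2 adds no limit. SAP 6.8.2, which dates a sustained event to the first qualifying measurement, adds none either.

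On sampling, Protocol 6.2.2 states: "Patients will have further visits with a reduced number of assessments two and four days thereafter if they are still hospitalised" (Days 3 and 5). The clinic visits are "Visits 3, 4 and 5 (EoT) on days 15, 30 and 90 respectively after randomisation". The Flow Chart lists eGFR at all of these and at the Early Discontinuation Visit.

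**The concern.** A confirmation rule exists to keep transient dips out of the endpoint. The death route is a reasonable substitute when a patient dies before confirmation was possible. As written, it also covers patients in whom later central samples were taken and showed recovery. Death from any cause then turns a disproved fall into a renal event, while the same eGFR values in a survivor would not count.

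Recovered dips are plausible here. Protocol 1.4.2 reports, from trials in diabetes, that "An initial decrease of estimated glomerular filtration rate (eGFR) was seen in patients treated with empagliflozin" and that it later improved. Protocol 3.2 makes renal function a focus of the safety assessment, and this composite is the only renal item among the listed secondary endpoints. If true renal events are few, a small number of false ones could be noticeable.

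**Working it through.** The documents give no expected number of renal events, so there is no plan figure to reproduce. The 87.4% power in Protocol 7.5 concerns the win ratio.

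**Inputs**

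- eGFR days and windows (Protocol Flow Chart): 3 (±1), 5 (±1), 15 (±3), 30 (±3), 90 (±7). Days 3 and 5 apply only if the patient is still in hospital.
- Death route conditions (SAP 6.6.2): no sample at +30 days or later, and death by +60 days.
- Planning values (Protocol 7.5): 250 per arm, 5% dead by Day 90 (taken here as the placebo rate), death hazard ratio 0.8.
- Assumptions not in the documents: constant death hazard over 90 days, and 5-20% of those who die having a qualifying fall that recovered.

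**Step 1: can a recovered Day 30 value block the rule?** The nominal gaps are 30 − 3 = 27, 30 − 5 = 25 and 30 − 15 = 15 days, all under 30. With visit windows, the gap to Visit 4 is:

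- from Visit 2b: 27 − 4 = 23 to 33 − 2 = 31 days (30 or more in 3 of 21 day combinations);
- from Visit 2c: 27 − 6 = 21 to 33 − 4 = 29 days;
- from Visit 3: 27 − 18 = 9 to 33 − 12 = 21 days.

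A recovered Visit 4 value therefore almost never blocks the rule.

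**Step 2: one patient.** eGFR falls 45% on Day 5, is normal on Days 15 and 30, and the patient dies on Day 60. The last sample is at +25 days and death at +55 days. Both conditions are met, and an event is recorded with date Day 5. With the same values, a patient alive and still recovered at Day 90 has no event.

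**Step 3: death days on which the rule counts a recovered fall (nominal schedule).** The last day is the fall day + 60.

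| Fall at | At least one recovered sample | All later samples before Day 90 recovered |
|---|---|---|
| Day 3 | Days 6-63 | Days 31-63 |
| Day 5 | Days 16-65 | Days 31-65 |
| Day 15 | Days 31-75 | Days 31-75 |

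After a Day 30 fall there is no scheduled sample before Day 90, so a recovery would not normally be seen.

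**Step 4: deaths in those windows.** Hazard h = −ln(0.95)/90 per day. Deaths by Day 90: 250 × 0.05 = 12.5 on placebo and 250 × (1 − 0.95^0.8) = 10.1 on empagliflozin, together about 22.6. Deaths after Day a and up to Day b: 250 × [exp(−ha) − exp(−hb)] on placebo, and the same with 0.8h on empagliflozin.

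- Days 31-63: 4.58 + 3.68 = 8.26
- Days 6-63: 8.11 + 6.51 = 14.62
- Days 31-65: 4.85 + 3.90 = 8.75
- Days 16-65: 6.96 + 5.60 = 12.56
- Days 31-75: 6.22 + 5.01 = 11.23

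The windows overlap and must not be added.

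**Step 5: misclassified events.** For the Day 3 windows, the low end is 0.05 × 8.26 = 0.41 and the high end 0.20 × 14.62 = 2.92. The Day 5 windows give 0.05 × 8.75 = 0.44 to 0.20 × 12.56 = 2.51. The Day 15 window gives 0.05 × 11.23 = 0.56 to 0.20 × 11.23 = 2.25. If 5% is applied to both arms, the Day 3 windows hold 2 × 4.58 = 9.16 and 2 × 8.11 = 16.22 deaths, giving 0.46 to 3.24.

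**The case against.** **Intent.** The rule stands under a subheading about a missing confirmatory measurement, within the missing-data section. A patient with normal values at Days 15 and 30 has contrary evidence, so the authors probably did not mean to count such a case. That is likely true, but the operative text gives two conditions and these patients meet both. Code that follows it will count them, and a programmer who did otherwise would be departing from the plan without a record. The protocol's footnote to the word sustained in 2.1.3 was not legible in the text available for this check. It was not relied on, and should be checked for a limit.

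**Reach.** A reader might infer that any recovery before death is ignored. That is wrong: a recovered sample at +30 days or later, including an unscheduled or early-discontinuation sample, blocks the rule. A reader might also infer that only in-hospital dips are affected. The Day 15 visit is an outpatient visit for a discharged patient and is affected too.

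**Bias.** A reader might infer that the rule works against empagliflozin. The documents do not support that. Protocol 1.4.2 gives no size for the initial decrease, nothing shows drug-related dips reaching 40%, and the same paragraph says renal impairment was similar to placebo. The planning hazard ratio of 0.8 for death would push the other way, since fewer deaths mean fewer false events on the active arm.

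**Importance.** The endpoint is one of ten secondary endpoints, without ranking or multiplicity control (Protocol 7.1 and 7.2.3, SAP 7.5.2). Renal safety is also read from the decreased-renal-function adverse event of special interest (Protocol 5.2.7.1.4), the acute renal failure and creatinine tables (SAP 7.8.1.3), and the eGFR models and shift tables (SAP 7.8.2). This stands: the composite alone would not decide the trial's view of renal safety.

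**Conclusion.** The point holds on the text of SAP 6.6.2. Falls at Days 3, 5 or 15 that central samples less than 30 days later show to have recovered are classed as sustained if the patient dies within 60 days of the fall and before a sample at +30 days or later. This is a stated rule that gives a wrong classification, not a missing detail.

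The likely size is about 0.4 to 3 patients. That rests on the protocol's mortality assumptions, a constant hazard, and an assumed 5-20% of those who die having a qualifying fall that recovered. The true share is unknown, and patients discharged before Days 3 and 5 lower the opportunity. Applying the 5-20% to all 22.6 expected deaths would overstate the effect, because only deaths inside the windows count.

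The consequence is limited to an exploratory secondary endpoint. The primary analysis is untouched, and neither the direction nor the presence of a between-arm bias is established. It is still worth correcting, because the change is small and the endpoint may have few events.

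**What to change.** In SAP 6.6.2, add a condition to the death rule: it applies only if no later central eGFR exists before death, or every later central eGFR before death also meets the same threshold. If a later value no longer meets the threshold, that fall is not sustained, and any new fall after it is assessed on its own date.

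The condition should cover every later value and not only the last one. With a fall, a recovery and a second fall before death, a last-value check would accept the first fall and, under SAP 6.8.2, date the event to it.

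Genuine unconfirmed falls before death still count. The cost is one or two sentences in the SAP and one condition in the derivation code, with no new data. It should be made before database lock and unblinding.

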6.6.3 Longitudinal Analyses

There will be different methods of analysing continuous longitudinal data.

Observed case on-treatment (OC-OT):

Only the available data that were observed while patients were on study medication (defined as time from first drug intake until last permanent treatment stop date plus the endpoint specific follow-up time (as defined in [Table 6.1: 2](#))) are considered.

Measurements are assigned to planned weeks according to [Table 6.7: 1](#)

Imputed records are not included.

Observed case including data after treatment discontinuation (OC-AD):

All available data are considered, including values obtained on treatment or post-treatment.

Imputed records are not included.

Measurements are assigned to planned weeks according to Table 6.7: 1.

6.7 BASELINE, TIME WINDOWS AND CALCULATED VISITS

Baseline will be defined as the last available measurement before start of randomised trial medication for all endpoints. For laboratory data (e.g. NT-proBNP), baseline will use central laboratory data.

Since the protocol specifies that all measurements are taken at Visit 2a before any intake of trial medication, all measurements at the first day of drug intake are assumed to qualify as baseline assessments.

For randomised patients without any treatment intake: Baseline will be defined as the last available measurement before or on the day of randomisation.

Measurements taken after the first intake of randomised trial medication will be considered on-treatment values if they have been obtained up to the end of the parameter specific follow-up period as defined in Table 6.7: 1 below and will be assigned to the randomised study drug for efficacy and safety analyses. Measurements taken after the end of the parameter specific follow-up period after the last intake of study drug will be considered post-treatment values.

Efficacy and safety measurements will be assigned to visits based on time windows around the planned visit dates. These time windows are defined based on the planned number of days after the date of first administration of study drug.

The time window for the first visit after randomisation starts on the day after the first intake of study drug. The midpoint between two on-treatment visits defines the end of a time window, with the midpoint being included in the time window of the preceding visit.

Table 6.7: 1 Time windows

Visit number	Visit label	Planned days	Time window (days after baseline)	
Endpoints assessed at each on-site visit (e.g. creatinine / eGFR)				
2a	Baseline ¹	1	NA	1
2b	Day 3	3	2	4
2c	Day 5	5	5	10
3	Day 15	15	11	22
4	Day 30	30	23	60
5	Day 90	90	61	Trt stop + x* days
Endpoints that are not assessed on Visit 2b and 2c (e.g. weight)				
2a	Baseline ¹	1	NA	1
3	Day 15	15	2	22
4	Day 30	30	23	60
5	Day 90	90	61	Trt stop + x* days

¹ Only values taken prior to the start of treatment with randomised study drug can be considered baseline values. Time windows will be used for assignment of measurements to scheduled visits.

* See [Table 6.1: 2](#)

Only one observation per time window will be selected for analysis at an on-treatment visit – the non-missing value will be selected which is closest to the protocol planned visit day. If there are two observations which have the same difference in days to the planned day or if there are two observations on the same day, the first value will be used.

Baseline definition for concomitant therapies

Concomitant medication taken at baseline is any medication with start date ‘continued’ or before date of first study medication intake (randomisation date will be used for patients not treated) and end date continued on or after date of first study medication intake (randomisation date will be used for patients not treated).

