6. GENERAL ANALYSIS DEFINITIONS

6.1 TREATMENTS

There will be three basic treatment phases in this trial: screening, study treatment phase (with either empagliflozin 10mg or matching placebo) and post-treatment. However, during the study treatment phase, patients are allowed to go off-treatment and subsequently re-start treatment. This may happen not at all or repeatedly for a given patient.

The purpose of the definitions below is to describe all the different study/treatment intervals, in which a patient can participate in during the course of the trial. Note that the term "treatment regimen" also covers the "off-treatment" time periods.

Table 6.1: 1 Treatment regimens / study intervals

Label	Interval	Start date
Screening	Screening	Date of informed consent
Placebo/ Empagliflozin 10mg	Treatment	Date of first administration of study medication
Off-treatment (if applicable)	During treatment interval, but not on treatment	Date of last administration of study medication before temporary discontinuation + 1 day
Placebo/ Empagliflozin 10mg (if applicable)	During treatment interval, after restart of study medication	Date study medication re-started
Post-treatment	Post-treatment	Date of last administration of study medication + 1 day

Details on the definition of the on-treatment period for different endpoints are listed in [Table 6.1:2](#). The efficacy analyses will follow the intention-to-treat (ITT) principle in assigning patients to treatment groups, i.e. patients will be analysed as randomised.

Safety analyses will also assign patients to the treatment group as randomised.

If a patient erroneously receives the wrong trial drug, all subsequent medication packs dispensed to the patient will still be for the treatment group to which the patient was randomised. Therefore, the adverse events will be analysed as per randomised treatment, which is expected to reflect the prevailing treatment.

In the exceptional case that a patient took the wrong treatment, adverse events may occur while being on the wrong treatment. Analyses of this data are described in [Section 7.8.1.6](#).

Table 6.1: 2 Endpoint specific assignment to the on-treatment phase

Endpoint	Last day of assignment to the on-treatment phase (days after last intake of study medication)
Adverse events	7
Safety laboratory measurements	3
Heart rate	1
Glycosylated haemoglobin (HbA _{1c})	7
Glucose	1
Body weight	1
Creatinine and estimated glomerular filtration rate (eGFR)	1

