N-terminal pro B-type natriuretic peptide (NT-proBNP)	1
Blood pressure (BP)	1
Patient reported outcome	7

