6.6 HANDLING OF MISSING DATA AND OUTLIERS

6.6.1 Imputation methods

There will be no imputation of data for safety analyses.

For patients who discontinue the trial treatment prematurely, all efforts will be made to follow patients for survival and for any other endpoints including the primary and secondary endpoints until the end of the trial.

Multiple imputations:

Missing data for the Kansas City Cardiomyopathy Questionnaire Total Symptom Score (KCCQ-TSS), as part of the stratified win ratio and NT-proBNP (log-transformed values) will be estimated using multiple imputation, according to whether patients are on-treatment or off-treatment.

Values measured after premature discontinuation of study drug will be included in the analyses. All available on- and off-treatment data up to the planned measurement at Day 90 will be included.

There will be different types of missing data to be considered for the imputation.

Table 6.6.1: 1 Adjusted multiple imputation “jump-to-placebo” approach – the missing data imputation method

Missing data imputation (Assumption of missingness)	Non-monotone	Monotone
On-treatment data	MCMC-MI ¹ (MAR ³)	SLR-MI ² (MAR)
Off-treatment ⁴ data	Jump-to-Placebo (MNAR ⁵)	Jump-to-Placebo (MNAR)

¹ Markov Chain Monte Carlo – Multiple imputation (MCMC-MI)

² Sequential linear regression – Multiple imputation (SLR-MI)

³ Missing at random (MAR)

⁴ Any instance of a patient discontinuing treatment will lead to all future measurements being considered as off-treatment.

⁵ Missing not at random (MNAR)

As the first step, the non-monotone on-treatment missing data will be imputed using Markov Chain Monte Carlo (MCMC) simulation and standard techniques; MI will be performed separately by treatment with baseline value as a continuous variable and HF status as a binary variable (de novo or decompensated chronic HF). One hundred imputations will be performed to ensure adequate efficiency and stability of the estimation for missing data. This step will be referred to as ‘MCMC-MI’.

For the monotone missing on-treatment data, a sequential linear regression MI approach will be used and referred to as ‘SLR-MI’. The MI will be performed on a data set only including on treatment data and once per imputation from the previous step. This procedure will impute values for all missing time points both on- and off-treatment, so imputations for off-treatment values will then be deleted. The regression models will be fitted separately by treatment and

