9.2 ALGORITHM FOR IMPUTATION ACCORDING TO JUMP-TO-PLACEBO METHOD

This algorithm imputes missing on-treatment data as MAR, and then imputes missing off-treatment data as MNAR by a jump-to-placebo method.

The conceptual approach is described by Carpenter et. al. (11). The implementation is planned as follows:

1. Remove any off-treatment data from dataset
2. Non-monotone missing data is imputed under MAR to create a monotone pattern
 - a. 100 imputations are performed by MCMC-MI, stratified by treatment, with the following parameters:
 - i. Baseline value included as a continuous variable, HF status as a binary variable (de novo or decompensated chronic HF)
 - ii. Multiple chains with 200 burn-in iterations per chain
 - iii. Jeffrey's prior
3. SLR-MI is used to impute missing monotone on-treatment data:
 - a. All data is imputed using SLR-MI, separately by treatment, with the following parameters:
 - i. Baseline (continuous), HF status (de novo or decompensated HF) included as covariates
 - ii. All imputed data for patients at an off-treatment time point is deleted
4. On-treatment group means are calculated for each imputation at each visit
 - a. ANCOVA used to calculate adjusted means with the following parameters:
 - i. Baseline (continuous), HF status (de novo or decompensated chronic HF), and treatment included as covariates
 - ii. Restricted Maximum Likelihood and Kenward-Rogers methods
 - iii. Least Square Means used
5. Placebo group on-treatment means at each visit are subtracted from all group on-treatment means at the same visit, to give treatment differences

- a. Note that these will be 0 for the placebo group
6. Individual data is ‘temporarily saved’ at this point, excluding available off-treatment data
7. Treatment differences are subtracted from the respective (by visit and treatment) data values
 - a. Results are the ‘residuals’ after removal of treatment effect(s)
 - b. This is referred to as the residual data
8. Subset of the residual data is created with all patients in placebo group and all patients with missing values at first visit requiring imputation. Note that these missing values will all be off-treatment.
9. Multiple imputation is performed on the first visit requiring imputation
 - a. Linear regression models are used to derive the distributional parameters;
 - i. One imputation per existing imputation
 - ii. Residual subset used

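### The only Day-90 window closes a few days after treatment stop, so read literally it shuts out the off-treatment Day-90 values that the all-data analyses are meant to use

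*SAP*

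**What the plan says.** SAP 6.7 assigns efficacy and safety measurements to visits by the windows in Table 6.7: 1. Both blocks of that table give Day 90 a window from Day 61 to "Trt stop + x* days". The asterisk leads to Table 6.1: 2 in SAP 6.1, whose column is headed "Last day of assignment to the on-treatment phase (days after last intake of study medication)". The row "Patient reported outcome" gives 7 days, other safety laboratory values have 3, and eGFR, heart rate and blood pressure have 1. The Day-15 and Day-30 windows end at fixed days, 22 and 60.

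SAP 6.6.3 defines two observed-case analyses. OC-OT is cut at the last permanent stop plus the endpoint's follow-up time. For OC-AD, "All available data are considered, including values obtained on treatment or post-treatment". Both are then assigned to visits by the same Table 6.7: 1.

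SAP 7.4 and Protocol 7.2.1 base efficacy on on- and off-treatment data. SAP 7.8.2 and 7.8.3 call for all-data analyses in the randomised set. On imputation, SAP 6.6.1 states: "All available on- and off-treatment data up to the planned measurement at Day 90 will be included". Footnote 4 of Table 6.6.1: 1 adds: "Any instance of a patient discontinuing treatment will lead to all future measurements being considered as off-treatment". Step 1 of SAP 9.2 is "Remove any off-treatment data from dataset", and step 12 puts observed off-treatment values back. Protocol 3.3.4.1 and footnote 3 of the Flow Chart keep patients who stop treatment in follow-up to Visit 5.

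**The concern.** A window that closes x days after treatment stop cannot hold the later post-treatment values that OC-AD exists to include. Only Day 90 is affected, and Day 90 is the KCCQ timepoint of the primary endpoint.

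For the OC-AD and all-data analyses nothing in the visible text overrides the table. Followed as written, it discards values that the protocol collects on purpose. The KCCQ-TSS mixed model in SAP 7.5.2 would then treat as missing a value that was observed.

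The primary win ratio has a narrower problem. Step 12 of SAP 9.2 restores observed off-treatment values without saying which one belongs in the Day-90 cell. The rule that picks one value per window in SAP 6.7 is written for on-treatment visits only. Two programmers could therefore fill the cell with an Early Discontinuation value or with Visit 5. Either could also find nothing inside the window and leave the jump-to-placebo imputation in place.

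**Working it through.** **Reproducing the table.** SAP 6.7 sets each window's end at the midpoint between adjacent planned visits, with the midpoint going to the earlier visit. For planned days 3, 5, 15, 30 and 90:

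- (3 + 5)/2 = 4
- (5 + 15)/2 = 10
- (15 + 30)/2 = 22.5, giving 22
- (30 + 90)/2 = 60

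These match the table, so the Day-90 window starts at Day 61. It is the only one whose end depends on treatment.

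**Inputs.** The upper limit is S + x, where S is the day of last intake and x comes from Table 6.1: 2. Visit 5 is Day 90 ± 7, so Days 83 to 97 (Protocol Flow Chart).

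**Conditions.**

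- The window is empty if S + x < 61, so S ≤ 60 − x.
- Every permitted Visit 5 date is excluded if S + x < 83, so S ≤ 82 − x.
- A value on Day 90 is excluded if S + x < 90, so S ≤ 89 − x.

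| Endpoint | x | Window empty | All Visit 5 dates excluded | Day 90 excluded |
|---|---|---|---|---|
| KCCQ | 7 | S ≤ 53 | S ≤ 75 | S ≤ 82 |
| Haemoglobin, haematocrit | 3 | S ≤ 57 | S ≤ 79 | S ≤ 86 |
| eGFR, heart rate, blood pressure | 1 | S ≤ 59 | S ≤ 81 | S ≤ 88 |

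**Example A, KCCQ.** Last intake is on Day 65, an Early Discontinuation KCCQ is taken on Day 66, and Visit 5 is on Day 90. The window is 61 to 65 + 7 = 72. It takes the Day-66 value as Day 90 and excludes the true Visit 5. With an end that does not depend on treatment stop, the distances from Day 90 are 24 and 0, so Visit 5 is chosen.

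**Example B, KCCQ.** Last intake is on Day 40. The upper limit is 40 + 7 = 47, below 61, so no value can be assigned to Day 90 even if Visit 5 took place.

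**Not affected.** Day-15 and Day-30 values are untouched, and so is the 30-day NT-proBNP AUC.

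**Undefined.** Patients who were randomised but never treated belong to the randomised set. They have no treatment stop, so their Day-90 limit is not defined.

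**The case against.** The best reply is that the table was written for on-treatment data and nobody would apply it otherwise. SAP 6.7 speaks of on-treatment visits when it sets the midpoints and when it selects one value per window, and x comes from a table of on-treatment limits. Cutting the all-data version at the same point would remove its difference from the on-treatment version at Day 90. This is probably how the row arose, and the text is not evidence that data will in fact be dropped. But SAP 6.6.3 expressly sends OC-AD to the table, and no other window is given.

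A second reply is that the primary endpoint is already covered: SAP 6.6.1 and step 12 include observed off-treatment values, and Protocol 3.1 places the primary assessment at Visit 5. The intent is indeed clear, and keeping an imputed value where one was observed would go against it. The choice of value is still open, because SAP 6.7 assigns values by time window and not by visit name.

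A third is that the consequences are modest. No analysis in the visible part of SAP Section 7 carries the OC-AD label. The plainest conflicts are the laboratory models and vital-sign summaries, for which no hypothesis test is planned, and the KCCQ-TSS mixed model is exploratory. All of this is fair and limits the weight of the point. That model is nevertheless covered by the general efficacy rule in Protocol 7.2.1 and SAP 7.4.

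One loose end also stands. A KCCQ within 7 days of last intake is on-treatment under Table 6.1: 2 but off-treatment under footnote 4 of Table 6.6.1: 1. Where Visit 5 exists, as in Example A, this does not change which value the proposed rule selects.

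**Conclusion.** The concern holds. As written, the Day-90 row contradicts the definition of OC-AD and the plan's stated use of on- and off-treatment data. For KCCQ, a value on Day 90 is excluded for last intake up to Day 82, every permitted Visit 5 date up to Day 75, and the window is empty up to Day 53. The corresponding days are 86, 79 and 57 for haemoglobin and haematocrit, and 88, 81 and 59 for eGFR, heart rate and blood pressure.

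These limits assume that the table is applied literally and that treatment stop means the last permanent stop, as in the OC-OT definition. Parts of the SAP are not public, so the conclusion concerns the visible text. For the win ratio the finding is an unspecified choice of value, not an intended exclusion. The documents give no discontinuation rate or timing, so neither the number of patients affected nor the size or direction of any effect on the win ratio can be stated.

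**What to change.** 1. In Table 6.7: 1, limit the treatment-stop bound to OC-OT. OC-OT results do not change, because its own definition already applies that cut.
2. For OC-AD, the all-data analyses in the randomised set, and the imputation and win-ratio dataset, end the Day-90 window at the patient's day of trial completion as defined in SAP 6.8.3. In practice this means Day 61 onward. It also gives untreated patients an upper limit.
3. In SAP 6.7, extend the rule of taking the value closest to the planned day to off-treatment visits, and have step 12 of SAP 9.2 cite this window and rule.
4. As a clerical correction, SAP 6.7 should point to Table 6.1: 2, not Table 6.7: 1, for the follow-up periods.

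Late on-treatment values are not lost. Drug supply is 35 + 2 × 35 = 105 days, so suppose last intake and Visit 5 both fall on Day 100. The present row runs to 100 + 7 = 107 and keeps the KCCQ; trial completion is Day 100 or later and keeps it too.

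The cost is one table row, one sentence in 6.7, one in step 12, one cross-reference and one programming rule. No new data are needed.
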